We will acquire standard anatomic scans during an initial 40 minutes period before experimental scans. The anatomic scans include: (1) a 3 plane localizer using a fast gradient echo sequence (TE/TR 1.7/32.1 ms); (2) a volumetric scan (3D Fast RF-spoiled gradient echo sequence with TE/TR 3.7/9.1 ms); (3) a 2D T1-weighted FLAIR scan of the slices to be acquired in the fMRI study (2D fast spin echo sequence with TE/TR 7/26ms), and; (4) an 8-shot EPI sequence of the slices to be acquired (TI/TE/TR 860/5.9/1977 ms). The EPI sequence and T1-weighted slices are used to align the fMRI data with the volume scan. For fMRI studies, we currently use the product EPI sequence with 64 by 64 data acquisition matrix, TE of 30 ms, TR of 2.2 sec, FOV 24 cm, slice thickness of 5 mm. 19 slices are acquired in an interleaved fashion (odd first, then even) for the entire time the paradigm is being performed. Following these standard MR scans subjects will perform a simple motor task cycling run (alternating 45 sec episodes of rest and hand-squeezing). This run represents a positive control for the cycling acquisition and analysis in every run.

D.2.2. Data analysis.

The HFH fMRI facility possesses real time fMRI acquisition and analysis software. [name] [181-183] has developed software for er-fMRI analysis [see also 168, 172, 173, 178]. A data analysis system, similar to the system at MSU/HFH, will be installed at M.U.M. This system will complement the AFNI system already running. The HFH software acquires fMRI images and other physiological data (pulse oximetry, respiration, electrocardiogram) on the same computer, allowing a synchronized time-stamp on all data sets. Each channel of acquired data contains a corresponding data file and a timing file. The time series from these other physiological variables will be used as real-time covariables in multiple linear regression, thereby statistically controlling for the contributions of breath rate and CO₂ to the overall BOLD effect.

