The sequence of analysis includes: (1) discarding the initial three scans of each run due to magnetic instability; (2) correcting for movement artifacts by the co-registration of the time series using AIR (automatic image registration); (3) morphing the distorted fMRI image onto the accurate, high resolution MRI anatomic image, by registering fMRI images to the 8-shot EPI scan using AIR and registering the T1-slice to the 3D-volume using image intensity; (4) generation of statistical parameter maps from the *t*-statistics resulting from the multiple linear regression—a statistical parameter map (SPM) is a map of all pixel areas that exceed a specified statistical threshold and; (5) transforming the *t*-statistic maps into *Z*-statistic maps for statistical analysis. With large numbers—100 or more—the *t*-distribution approximates a *Z*-distribution [184]. These final statistical parameter maps will reflect significant fluctuations in signal intensity during the two conditions of the cycling tasks, after the contribution of other physiological variables have been statistically removed.

D.2.3. Statistical analysis.

One of the valuable characteristics of fMRI is that the relatively high signal to noise ratio allows detection of significant changes in signal intensity *within* a single subject [185]. The steps for statistical analysis of all data will include:

- (1) The SPM [184] for the runs in each condition will be examined. Areas of significant signal fluctuations will be determined using two criteria [92]: (a) the *Z*-statistic > 4.0, ($p < 10^{-7}$), and (b) the cluster must contain a minimum of four pixels that touch on the sides or corners (eight-neighborhood connectivity).
- (2) We will examine the first run for possible adaptation effects. If the first run differs significantly from subsequent runs, we will consider excluding the first run from the overall analysis.
- (3) The *Z*-statistic of significant areas of fluctuations in signal intensity are noted when they meet the criteria above and are in 2 of the 3 statistical parameter maps from multiple runs in the same condition.
- (4) These *Z*-statistics will be used in parametric analyses.

D.2.4. Sample size.

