The BOLD signal and physiological measures will be collected during four runs of 12 minutes duration each. Each 12 min run comprises three periods: 5 min uninterrupted meditation, 5 min structured breath-holding, and 2 mins non-task, eyes-closed (EC) control. The meditation period are free running with no interruptions from experimenters. During the meditation period we expect 3-5 SBQ periods. The breath-holding periods are structured by duplicating the previous SBQ pattern by voice command from experimenter, the onset and offset of IBH corresponding to SBQs time frame for each subject. The non-task control period will be determined from the outcome of experiment 1 (Aim 1), and either be passive-attending or mental-counting. The physiological measures will include respiration and transcutaneous CO₂ measurements. Four runs will take 48 minutes, or about 1 hr due to 30 rest periods between conditions. Therefore, each fMRI session will last about 90 minutes per subject.

D.6.4. Event-related fMRI analysis (Hypotheses 1-3).

Er-fMRI methodologies will be used to probe brain mechanisms during the onset of two conditions, during SBQ and IBH periods. The scans will be aligned relative to the onset of either SBQ or IBH during the four runs to permit signal averaging: 4 images before (12 secs) and 4 images after onset (12 secs). A TM meditator, selected in our screening protocol, may exhibit 25-30 spontaneous breath-quiet periods in a 30-min TM session [9, 20-22]. We estimate 12-20 periods will occur in our four meditation periods.

Images from individual runs will first be normalized to correct for the range of intra- and inter-subject signal intensity and temporal drift [171]. Specifically, normalization will involve: (1) scaling of signal intensity to a fixed value of 1000; (2) linear slope removal in a voxel-by-voxel basis; (3) spatial filtering with a one-voxel radius Hanning filter, and; (4) removal of the mean signal intensity on a voxel-by-voxel basis. The normalized fMRI images will then be aligned relative to the onset either SBQ or IBH periods. These images will be averaged within each subject. The mean image for each subject will be transformed into stereotaxic atlas space [208] using the highest point of the mid-sagittal plane and the anterior and posterior commissures. The atlas-transformed matrices will then be averaged across subjects.

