D.6.5.1. Sequence of Analysis. First, we will create a dummy time-series of 1, or 2's that correspond to the scans before and during three conditions: IBH, SBQ or EC. The dummy time-series then will be convolved with the hemodynamic response model using the Cohen Model. This will yield the dummy independent variable that will be entered into the multiple linear regression analysis along with O₂ and CO₂ data. The scans for each of the periods will be dependent variables in the analysis. We will examine the resulting statistical parameter maps for clusters of pixels displaying significant fluctuations in signal intensity. The Z-statistic of the activated clusters that meet our criteria (D.2.3.) will be entered as variates in a repeated-measures ANOVA, with brain area as the factor and the period as the repeated measures.

D.6.5.2. Comparison between conditions: SBQ, IBH and EC. Condition differences will be assessed with two-way repeated measures ANOVA with brain areas and condition as factors, and the two periods (before and during the conditions) as the repeated measures. Individual comparison will be conducted if there are significant main effects.

- We expect no main effects for brain areas, indicating highly variable activation across brain areas yielding no consistent relations.
- We expect main effects for condition (SBQ, IBH, EC), indicating different brain mechanisms are active during each condition. For example, during IBH we expect higher levels of task effort and motor system activation, and possibly higher CO₂ levels to yield the predicted main effect.
- We expect main effects for the repeated measure (before and during). The 'before' periods may be somewhat similar, while the 'during' periods may be significantly different.
- We expect significant interactions, indicating differential involvement of some brain areas during the three conditions. For instance, the cerebral cortex may exhibit lower BOLD signal in both 'before' periods. However, the cortex is expected to be activated during IBH, while remaining low or reduced during SBQ.

D.6.6. Outcome. This experiment will help identify:

- (1) Neural mechanisms specific to the generation and maintenance of IBH, and the effects of hypercapnia and loss of mechanical respiratory activity on BOLD signal intensity.
- (2) Neural mechanisms specific to SBQ periods, as compared to a variety of brainstates, including, other meditation periods, IBH, and EC.

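### The map statistics come from multiple-regression t-values with no listed allowance for serial correlation between scans, so areas reported at Z > 4.0 may rest on weaker evidence than the figure implies

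*Protocol*

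**What the plan says.** Protocol D.2.2 lists five steps from scans to decision statistic, opening with "The sequence of analysis includes: (1) discarding the initial three scans of each run due to magnetic instability". The others are motion correction, registration to anatomy, maps of t-statistics "resulting from the multiple linear regression", and conversion of t to Z. The reason given for the conversion starts "With large numbers—100 or more—the" and says that the t-distribution then approximates the Z-distribution.

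D.2.3 counts an area as significant when Z exceeds 4.0 and "the cluster must contain a minimum of four pixels that touch on the sides or corners". Its Z is noted if the area appears in two of three maps for the same condition, and these Z values go into parametric analyses. D.5.4 uses them in the MANOVA for Hypotheses 1 and 2.

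For the state-related analysis, D.6.5.1 convolves a dummy series with the haemodynamic model to give a variable "that will be entered into the multiple linear regression analysis along with" the blood-gas data. Clusters meeting the D.2.3 criteria go into a repeated-measures ANOVA.

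D.2.1 gives "TR of 2.2 sec, FOV 24 cm, slice thickness of 5 mm". D.6.4 counts "4 images before (12 secs) and 4 images after onset (12 secs", which implies 3 s per image.

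The temporal handling described is physiological covariates in the regression (D.2.2, D.6.2.1, D.6.5.1) and, for the event-related analysis, linear slope removal (D.6.4). Autocorrelation, prewhitening and effective degrees of freedom are not mentioned.

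**The concern.** The t-statistic of an ordinary regression is correctly scaled only if the residuals are independent. Successive scans of one voxel a few seconds apart are likely to be positively correlated, and the regressors here are slow blocks. Positive correlation puts extra noise variance at exactly the slow time scale of the contrast, and the ordinary standard error misses it. Justifying the conversion by a count of 100 or more treats every scan as a full piece of independent information, so it does not meet the problem.

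Two things are at stake. First, the Z > 4.0 filter decides which areas are carried forward for Hypotheses 1, 2, 6 and 7. If Z is too large, areas pass on weaker evidence than stated. Second, D.5.4 and D.6.5 compare Z between brain areas. If autocorrelation differs by area, part of the difference in Z reflects noise structure and not the size of the response.

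**Working it through.** **The plan's own figure.** D.2.3 labels Z > 4.0 as p below 10^-7. The normal tail area at 4.0 is 3.2e-5 one-sided and 6.3e-5 two-sided; p = 10^-7 needs Z = 5.20 one-sided or 5.33 two-sided. The label does not reproduce even with independent scans. That is a separate error and is not used as support below. The baseline here is 3.2e-5.

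**Inputs for Aim 1.** D.5.3 gives 45 epochs, 15 per condition, with 30 s as the example. 45 × 30 s = 1,350 s, and 1,350 / 2.2 = 613.6, so 614 scans, or 611 after dropping three.

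Assumptions: AR(1) residuals with lag-one correlation rho (the documents give none), a gamma-variate response, random block order, a linear trend term and no physiological covariates.

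**Formula.** With design matrix X, contrast c between two conditions and residual correlation matrix V, the ratio of the true to the ordinary least squares standard error is

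sqrt{ c'(X'X)^-1 X'VX (X'X)^-1 c / ( E[s²] · c'(X'X)^-1 c ) }, with E[s²] = trace(RV)/(n − p), R being the residual-forming matrix.

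For very slow blocks this approaches sqrt((1 + rho)/(1 − rho)), which can be checked by hand. For rho = 0.3 it is sqrt(1.3/0.7) = 1.363, against 1.35 from the design itself.

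**Results, 30-s epochs, TR 2.2 s, averaged over random orders**

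| rho (assumed) | SE ratio | True Z when reported Z = 4.0 | One-sided p | Multiple of 3.2e-5 | Reported Z needed for a true 4.0 |
|---|---|---|---|---|---|
| 0 | 1.00 | 4.00 | 3.2e-5 | 1 | 4.0 |
| 0.1 | 1.10 | 3.63 | 1.4e-4 | 4 | 4.4 |
| 0.2 | 1.22 | 3.29 | 5.1e-4 | 16 | 4.9 |
| 0.3 | 1.35 | 2.97 | 1.5e-3 | 48 | 5.4 |
| 0.4 | 1.50 | 2.67 | 3.8e-3 | 119 | 6.0 |
| 0.5 | 1.68 | 2.38 | 8.6e-3 | 272 | 6.7 |

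True Z is 4 divided by the unrounded ratio; the last column is 4 times that ratio.

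**Sensitivity.** At rho = 0.5 the ratio is 1.64 for 20-s and 1.70 for 40-s epochs at TR 2.2 s, and 1.60 to 1.68 across the three epoch lengths at TR 3 s. At rho = 0.1 it is 1.10 throughout. The conflict between 2.2 s and 3 s therefore does not change the conclusion.

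**Aim 2.** The breath-quiescent periods are irregular, so a layout has to be assumed. D.6.3 expects 3 to 5 periods in each 5-min meditation and D.6.2 gives durations of 10 to 40 s. Four such periods, at TR 2.2 or 3 s, give ratios of about 1.10 to 1.63 over the same range of rho.

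**Comparison between areas.** If one area has rho 0.1 and another 0.4, equal correctly standardised effects give reported Z values in the ratio 1.50 / 1.10 = 1.36.

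**The case against.** The strongest reply is that this is an omission and not a stated error. The D.2.2 list is introduced as what the sequence includes, names no error model, and passes estimation to site software whose treatment of serial correlation cannot be seen. An unseen analysis plan could also supply a correction. This stands in part: a reader might infer that the protocol fixes an independence model and closes off any correction, and the text does not support that. What remains is that the protocol itself gives the regression, the conversion with its reason, and the threshold, and that following those steps literally yields standard errors that are too small whenever residual autocorrelation is positive.

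The size is also conditional. The documents give no rho, the result runs from no effect at rho = 0 upwards, and the physiological covariates may absorb part of the correlation.

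Two further inferences are tempting and should not be drawn:

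- **A count of false areas.** Multiplying the single-voxel tail area by all 64 × 64 × 19 = 77,824 acquired positions would not give it. Many positions may lie outside the brain, and the four-pixel and two-of-three-maps rules remove chance exceedances. Those rules do work on the same inflated maps, so they reduce the problem without curing it.
- **Invalid later F tests.** The MANOVA and ANOVA use Z values as data. A multiplier common to all of them cancels from the F ratio and does not by itself raise the false-positive rate.

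**Conclusion.** The concern holds as a conditional one. Under positive residual autocorrelation, the procedure as written overstates Z in both aims. For an assumed AR(1) coefficient of 0.1 to 0.5 the standard error in Aim 1 is too small by a factor of about 1.10 to 1.68, so the Z > 4.0 rule operates at a true Z of about 3.6 to 2.4. Aim 2 is similar under the assumed layout. The direction follows from the slow-block design; the size depends on a coefficient that must be estimated from the data and could be smaller once the covariates are in the model.

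The practical consequence is confined to selection of areas on weaker evidence than stated and to distorted comparisons between areas with different autocorrelation. It should be corrected, but it does not invalidate the design.

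**What to change.** Insert a step before step (4) of D.2.2, and make the same change in D.6.5.1: with the physiological covariates in the model, estimate the residual autocorrelation for each voxel and prewhiten, for example by AR(1) generalised least squares. Alternatively, keep the ordinary estimates and correct the standard error and the effective degrees of freedom. Only then convert t to Z, using the effective degrees of freedom and not the scan count, and apply the D.2.3 criteria. If the software already does this, say so and name the error model.

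The cost is one routine processing step and, in some maps, fewer pixels above threshold. No extra scanning is needed.

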We will record fMRI (in first 10 subjects meeting inclusion criteria) during randomly ordered epochs of controls and TM practice. We will use two cycling ABC-run with eyes-closed. Each ABC-run comprises TM and two control conditions: (1) listening passively to nature (ie, ocean) sounds or (2) mental-counting by '2s'. An ABC-run (for example, using 30 sec epochs) will last about 22min, including 45 total epochs, 15 epochs each condition. This will result in 22 min/run x two epoch lengths = 45 min of testing, plus 40 min of preliminary anatomic scans, for a total time of less than 2 hr per MRI session. Whole-brain scans will be recorded from 19 slices per scan. At the end of each 22-min run, subjects will be asked to report their experiences. Carryover effects will be minimized by: (1) inserting one minutes breaks between runs. During these breaks we will be speaking and de-briefing the subjects; and (2) randomly presented control conditions in the same run. With this design, *within*-sets comparison will provide an estimate of the *minimal* carryover effects and *across*-sets will provide an estimate of *maximal* carryover effects.

D.5.4. Analysis for Hypotheses 1 & 2.

The data will be processed, and clusters of significant fluctuations in signal intensity will be noted (see Sect. D.2.2-D.2.3.). We expect clusters of fluctuations in signal intensity in 4-8 brain areas (see Sect. B.). The Z-statistics for areas of significant fluctuations in signal intensity will be noted from all runs and used as the variate in a repeated measures MANOVA. In this MANOVA, brain areas (4-8 estimate), and epoch condition (3) will be the factors, and the epoch-lengths (2) will be the repeated measure. For all main effects, individual comparisons will be conducted.

1. We expect **main effects for brain areas**, indicating significant differences in signal intensity between one or more brain areas. These changes may include in rank order: basal forebrain increases, slight cerebral and cerebellar cortex and mesencephalic reticular formation decreases, and no decreases in medial thalamus.
2. We expect **main effects for epoch condition**, indicating significant differences in signal intensity across the three different conditions—TM, passive-attending and mental-counting. These changes may include in rank order: de-excitation will be maximum for TM, then passive-attending, and lastly, mental-counting.

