3. We expect **main effects for the repeated measures**, indicating the epoch length that best framed the initial de-excitation of TM practice. For example, longer epoch lengths run the risk of introducing new, and variable cognitive and brain processes. This variability could result in lower signal-to-noise ratio, low signal intensity and more variance in the statistical test.
4. We expect **significant epoch length x epoch condition interactions**. We expect less cognitive and brain variability in the shorter epoch length regardless of condition resulting in greater distinction between epoch conditions. On the other hand, the greater variability of the longer epoch length may diminish the measured difference in signal intensity between conditions.

D.5.5. Outcome.

At the conclusion of this analysis, we should have empirical data sufficient to recommend the epoch length and the control condition to successfully image the initial de-excitation substate of TM practice. Secondary outcomes include consistency of signal intensity for regions of interest within subjects, and variability across runs between subjects. Anatomically, based on previous research-driven neural models (see Sect. B.2.5.), we would expect to at least find cortical de-excitation with possible exceptions of medial and ventral prefrontal cortices, accompanied with some basal forebrain, basal ganglia and brainstem excitation, cerebellar de-excitation and no change in medial thalamic activity.

D.5.6. Conclusion of Aim 1 Experiment.

From this experiment, we expect to find four basic outcomes regarding brain mechanisms during meditation from an ABC-cycling protocol:

- (1) The epoch length that appears to best frame the de-excitation process;
- (2) The effects of two different control conditions;
- (3) The brain areas that appear most closely correlated with the de-excitation process, as measured by the ABC-cycling protocol; and
- (4) The intra- and intersubject variability of activation/deactivation patterns;

Collectively, these findings will help formulate a working model of brain mechanisms during the de-excitation substate of TM practice.

D.6. Examine the Patterns of Neural Activity during the Maximum De-Excitation Substate (Aim 2).

Experiment 2: Comparing BOLD patterns across periods of differing mental & blood-gas conditions

D.6.1. Hypotheses. We will test five hypotheses in this experiment.

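### The Z > 4.0 cut-off states neither sign nor contrast, and the pooled condition main effect does not reliably test the Hypothesis 2 ranking

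*Protocol*

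**What the plan says.** **Selection rule.** D.2.3 sets the first criterion for carrying an area forward: "Areas of significant signal fluctuations will be determined using two criteria [92]: (a) the *Z*-statistic > 4.0". The second is a minimum cluster of four touching pixels. The Z values of areas that pass go into the parametric analyses. On which map the rule is applied, D.2.3 says only: "The SPM [184] for the runs in each condition will be examined". D.2.2 describes the final maps as showing "significant fluctuations in signal intensity during the two conditions of the cycling tasks", whereas the Aim 1 design has three conditions. No contrast is named.

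**Test.** In D.5.4 the selected Z values are the variate in a repeated-measures MANOVA with brain area and epoch condition as factors and epoch length as the repeated measure. Under the expected main effect of condition, D.5.4 gives the ranking: "de-excitation will be maximum for TM, then passive-attending, and lastly, mental-counting". Individual comparisons are tied to main effects. The only interaction predicted for Aim 1 is between epoch length and condition.

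**Predicted directions.** D.5.4 lists "basal forebrain increases, slight cerebral and cerebellar cortex and mesencephalic reticular formation decreases, and no decreases in medial thalamus". D.5.5 expects cortical de-excitation with possible prefrontal exceptions, together with "some basal forebrain, basal ganglia and brainstem excitation, cerebellar de-excitation and no change in medial thalamic activity". Section A describes the Aim 1 substate as an overall fall in brain excitation. De-excitation is nowhere defined as a signed quantity.

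**The concern.** The quantity of interest in Aim 1 is mostly a fall in signal, yet the cut-off as written admits only values above +4.0. If the coding is meditation minus control, a falling area has negative Z and does not pass.

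If the cut-off is instead taken as two-sided, the main effect of condition averages over areas expected to rise and areas expected to fall. An average of that kind can be small, zero or of the wrong sign when every area does what was predicted.

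At stake is the reading of Hypothesis 2. D.5.5 uses the same analysis to recommend a control condition, and D.6.3 carries that choice into Year 2 as the eyes-closed control. The D.2.3 criteria are also reused in the Aim 2 state-related analysis (D.6.5.1).

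**Working it through.** **The plan's own figure.** D.2.3 prints p < 10⁻⁷ beside Z > 4.0. The normal tail gives 1 − Φ(4.0) = 3.2 × 10⁻⁵ one-sided and 6.3 × 10⁻⁵ two-sided; p = 10⁻⁷ needs Z = 5.20 or 5.33 respectively. The printed value fits neither, so it cannot tell us which sidedness was meant. The mislabelled p-value is otherwise a separate matter.

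**Reading 1: the cut-off is signed.** Assume meditation-minus-control coding and an observed Z that is normal with SD 1 around a true area value μ. The values of μ are assumptions.

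- As written, P(kept) = 1 − Φ(4 − μ).
- With |Z| > 4.0, P(kept) = 1 − Φ(4 − μ) + Φ(−4 − μ).

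| True area Z | Kept as written | Kept if two-sided |
|---|---|---|
| −4 | 6.2 × 10⁻¹⁶ | 0.50 |
| −5 | 1.1 × 10⁻¹⁹ | 0.84 |
| −6 | 7.6 × 10⁻²⁴ | 0.98 |

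On the D.5.4 list this affects three of the four areas predicted to change. With the coding reversed, the same probabilities apply to the predicted increase instead.

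**Reading 2: both signs are kept.** From the D.5.4 list, set the basal forebrain increase to 1, each of the three decreases (cerebral cortex, cerebellar cortex, mesencephalic reticular formation) to r, and the medial thalamus to 0. The protocol gives no sizes, so r is an assumption; taking the thalamus as unchanged is also one.

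- Mean over areas = (1 − 3r)/5.
- Equal effects, r = 1: (1 − 3)/5 = −0.40. For an area effect of Z = 4.5 that is −1.8.
- D.5.4 calls the decreases *slight*. At r = 1/3: (1 − 1)/5 = 0.
- Below r = 1/3 the mean is positive.

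For the ranking, suppose each condition scales this whole pattern by a factor s, largest for TM, then passive-attending, then counting. Each condition mean is s(1 − 3r)/5. At r = 1/3 all three means are 0 and there is no main effect, although every area shows the predicted order. Below 1/3 the order of de-excitation in the pooled means reverses. Above 1/3 it is right but diluted.

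The cut-off also interacts with r. Decreases one third the size of the increase pass |Z| > 4.0 only if the basal forebrain Z exceeds 3 × 4.0 = 12. At a basal forebrain Z of 4.5 each decrease is −1.5 and is not selected; only the increase remains and the mean of selected areas is +4.5.

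**The D.5.5 list**, equal effects: three areas up, two down, one unchanged gives (3 − 2)/6 = +0.17. That counts all cortex as one area. With cortex as two clusters it is (3 − 3)/7 = 0; as three, (3 − 4)/8 = −0.125. The sign follows the cluster count, which D.5.4 puts at 4 to 8 areas in total without allocating them.

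**The case against.** **Both signs were probably intended.** D.2.3 calls its target fluctuations, a word without direction. The pilot maps showed positive and negative correlations, and D.5.6 lists activation and deactivation patterns as an outcome. A Z has a sign only relative to a contrast, and a fall in one contrast is a rise in the reverse one. A reader might infer that the plan throws away every decrease; the documents support only an unclear rule that does so on its literal reading under one coding. This part of the objection stands.

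**The two problems cannot occur together.** If only Z > 4.0 survives, no decreases are left to cancel. If decreases survive, the cut-off complaint falls. This also stands.

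**The ranking can be derived from the planned model.** Area and condition are both factors, so area-by-condition contrasts can be formed, and a net mean is a defensible readout of an overall decrease. A reader might infer that Hypothesis 2 is untestable; that goes too far. But D.5.4 attaches the ranking to the main effect and names no area-by-condition effect for Aim 1, whereas D.6.5.2 does predict such interactions for Aim 2.

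**The brainstem lists need not contradict.** A fall in mesencephalic reticular formation is compatible with excitation in some other part of the brainstem. A reader might infer that either brainstem result would count as confirmation; the wording is loose but does not establish that.

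**Sidedness and contrast coding are often left to an analysis plan, and this is an exploratory grant.** True, and D.5.4 hedges its ranking. But here the protocol states a cut-off and a test, and the point concerns those.

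**Conclusion.** The point holds as two alternative defects. On the literal reading with meditation-minus-control coding, areas with true Z of −4 to −6 have a chance below 10⁻¹⁵ of being carried forward. On the two-sided reading, the pooled main effect offsets predicted rises against predicted falls: −0.40 of a single-area effect on the D.5.4 list with equal sizes, and 0 if each decrease is one third of the basal forebrain increase. On neither reading is the stated main effect a reliable test of the ranking.

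The pooled figures rest on assumed effect sizes, on treating each listed region as one area and, apart from the cut-off illustration, on all areas being retained. They show that the result depends on quantities the protocol does not fix; they do not predict what the data will show. In particular, the +0.17 from the D.5.5 list might be read as proof that the plan points the wrong way; it vanishes or changes sign once cortex is counted as more than one cluster.

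**What to change.** 1. In D.2.3, change criterion (a) to |Z| > 4.0 with the sign retained, and name the contrast, allowing for three conditions in Aim 1.
2. In D.5.4, test the order TM, passive-attending, counting through area-by-condition contrasts within pre-named areas, or after multiplying each area's value by its predicted sign, in place of the pooled condition main effect.
3. Reconcile the D.5.4 and D.5.5 lists into one signed prediction per area, with mesencephalic reticular formation separate from other brainstem areas.

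The first change alone is not enough, because the pooled mean can still cancel. All three need only wording and analysis code, with no new data. The price is a doubling of the nominal per-pixel false-positive rate at the same threshold, 2 × 3.2 × 10⁻⁵ ≈ 6.3 × 10⁻⁵ (from unrounded values), and additional comparisons if the ranking is tested area by area.
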